#### **2.4 Study Flowchart**

	<pre> graph TD     A[Screening and Informed Consent Study Group: Within 24 hours of first tedizolid dose Control Group: Within 28 days of first tedizolid dose] --> B[Administration of tedizolid phosphate Study Group: 200mg orally q24h x 3-6 doses Control Group: 200mg orally q24h x 3 doses]     B --> C[Blood sample collection around final dose (0, 1, 2, 2.5, 3, 3.5, 4, 6, 8, 12, 16, 20, and 24 hours) Dialysate sample collection around final dose (0, 1, 2, 3, 4, 5, 6, 7, 8, 9, 10, 11, 12, 16, 20, and 24 hours)]     C --> D[Study Exit Physical and Labs]     D --> E[Data Analysis]     E --> F[Final Report]     subgraph At_steady_state [At steady state]         C     end </pre>
2.5 Study Procedures	
2.5.1 Screening Procedure
 
2.5.1.1 Study Group
 
Electronic medical records of admitted diabetic patients who are being followed by podiatrists for infections of the lower limbs will be pre-screened to identify patients eligible for study enrollment through evaluating each patient's profile for the meeting of inclusion and exclusion criteria. Pre-screening will involve accessing patient's medical record to determine eligibility. If eligible, written informed consent will be obtained (see 2.5.2) followed by complete screening, which will include a physical exam, medical, surgical, and medication history and collection of blood and urine for laboratory assessment (see 2.5.5.1). Screening will occur within 24 hours of the first dose of tedizolid.
 
2.5.1.2 Control Group
 
Adult healthy volunteers will be identified via hospital and local advertisements (newspaper, postings, and internet) and will be initially pre-screened via phone interview. If eligible, all volunteers will be screened by a study physician within 28 days of the scheduled study period to confirm that inclusion and exclusion criteria are met after providing written informed consent (see 2.5.2). This will include a physical exam, medical, surgical, and medication history and collection of blood and urine for laboratory assessment (see 2.5.5.1).
 
2.5.2 Informed Consent
 
Prior to study enrollment, patients and healthy volunteers identified as eligible for the study will be approached for consenting, where they will be provided with written informed consent that will document their election and agreement to participate in the study. The consenting process will be conducted by the principal investigator, co-investigators, or trained research staff members. A copy of the signed consent will be provided to the participant and placed in the medical record (study group only).

### **2.5.3 Study Drug**

All participants will receive tedizolid phosphate 200 mg orally every 24 hours. The study group will receive 3-6 doses, to allow flexibility in sample collection among other medical/surgical interventions required during his/her hospitalization. The control group will receive 3 doses to achieve steady-state before sample collection. All participants in the study group will also receive standard intravenous or oral antibiotic therapy to treat their diabetic foot infections.

### **2.5.4 Summary of Interventions**

- Screening physical exam and baseline blood and urine laboratory assessment
- Administration of oral tedizolid phosphate to achieve steady-state
- Insertion of microdialysis probe by study physician (see 2.5.5.3)
- Collection of blood samples
- Collection of dialysate samples
- End of study physical exam and blood and urine laboratory assessment

### **2.5.5 Procedures**

#### **2.5.5.1 Baseline Participant Evaluations**

At screening, eligibility will be verified using inclusion/exclusion criteria. A general physical examination, including pedal pulses (study group only), a medical/surgical/medication history and vital signs (temperature, blood pressure, heart rate, respiratory rate) will be conducted by the study physician. Clinical laboratory tests, including serum electrolyte panel, serum creatinine, liver function panel, complete blood count with differential, glycosylated hemoglobin (HbA1c)(study group only), albumin, and microscopic urinalysis will be performed unless drawn within the last three days and the participant is clinically stable. Urine pregnancy tests will be required for women of childbearing potential. Concomitant medications will be recorded. A blood sample for screening of common drugs of abuse (cocaine, tetrahydrocannabinol (THC), opiates, benzodiazepines, and amphetamines) will be collected (control group only).

Study group participants will be screened within 24 hours of first dose of tedizolid. Control group participants will be screened within 28 days of first dose of tedizolid.

#### **2.5.5.2 Clinical Research Center (CRC) – (Control group only)**

Once enrolled and confirmed eligible at baseline screening, control group participants will be admitted to the CRC at Hartford Hospital on the evening of Study Day -1. A second screening of selected control group participants, which will include a brief physical exam, vital signs, medical history, and repeat of all labs tested in 2.5.5.1 except for drugs of abuse screening, will take place. This is to confirm study eligibility is maintained. Study drug will be administered on Study Days 1, 2, and 3. A microdialysis catheter (see 2.5.5.3) will be inserted on Study Day 3, followed by blood and dialysate collection (see 2.5.5.5 and 2.5.5.6). A final end of study physical exam and collection of blood and urine for laboratory assessment will be conducted on Study Day 4 before discharge. On Study Days 1 and 2 (only), participants are permitted to leave the CRC for work/school or at discretion of the Principal Investigator after oral dosing and a 4 hour monitoring period. Participants must return to the CRC for dinner time (7pm) on the same day. During the remainder of the study (Day 3 and Day 4), participants will not be permitted to leave the CRC. Lunch and Dinner will be provided for participants while they are in the CRC. Participants must refrain from consuming caffeinated and alcoholic beverages during the study (Day -1 to Day 4)..

#### 2.5.5.2 Microdialysis Procedure

A microdialysis probe (63 MD catheter; MDialysis Inc., N. Chelmsford, MA) with a membrane length of 30 mm and molecular cut-off of 20 kDa will be inserted into subcutaneous tissue near the margin of the wound (study group) or healthy thigh tissue (control group) via a guidance cannula, following a local injection of lidocaine 0.5% solution to minimize pain. Specifically, for the study population a puncture hole will be made 10 cm away from the margin of the wound, in order to place the semi-permeable probe at the tip of the catheter within 5 cm of the wound (i.e., per-ulcer area). The microdialysis probe will be inserted just prior to the final planned tedizolid dose in all participants. The guidance cannula will then be removed, leaving the microdialysis probe implanted subcutaneously.

The microdialysis system will be connected and constantly perfused with lactated Ringer's solution (perfusate) at a flow rate of 2  $\mu$ L/min with a microinfusion pump (CMA 107 microdialysis pump, CMA Microdialysis AB, Solna, Sweden). After a 30-minute baseline sampling period, sampling of the interstitial fluid will begin before the start of the final dose of oral tedizolid for baseline values. At the beginning of the final dose, sampling will occur as noted in section 2.5.5.6. Once dialysate sampling is complete, the probe will be calibrated by the retrodialysis technique over a 1-hour interval to assess recovery of the antibiotic through the dialysis membrane. A calibration standard concentration of tedizolid 100  $\mu$ g/mL will be added to the perfusate and its rate of disappearance through the membrane will determine the recovery rate by obtaining a dialysate sample. Recovery of tedizolid via retrodialysis will be calculated as follows: % Recovery = 100 – (Concentrationdialysate / Concentrationperfusate × 100).

#### 2.5.5.4 Study Drug Administration

Tedizolid 200 mg will be administered by the oral route every 24 hours for 3-6 doses (study group only) or for 3 days (control group only). The doses will be administered by the nursing staff on the morning of the study days with a glass of water. Each dose will be preceded by an 8-hour fast and followed by a 4-hour fast. A record log of the date and time of administration will be maintained.

#### 2.5.5.5 Plasma Sample Collection

Blood samples to assess tedizolid concentrations will be collected over a 24-hour period after the final dose. Blood samples of 10 mL each will be collected through a Jelco® catheter at pre-determined time points. Blood sample times will be at 0 (just before administration of the final dose), 1, 2, 2.5, 3, 3.5, 4, 6, 8, 12, 16, 20, and 24 hours. Blood samples will be collected in a 10-mL BD Vacutainer® containing sodium heparin (green top). All blood samples will be immediately centrifuged (2,000  $\times$  g for 10 min) to collect the separated plasma, which will be stored in amber-colored polypropylene tubes to protect from light at -80 °C until concentration determination.

#### 2.5.5.6 Dialysate Sample Collection

Interstitial fluid concentrations of the soft tissue in the lower extremity will be assessed by *in vivo* microdialysis. Participants will refrain from excessive movement during the sampling process. After catheter insertion, the probe will be perfused with lactated Ringer's solution for 30 minutes prior to sampling. A baseline dialysate sample (120  $\mu$ L) will be taken over an hour after placement of the microdialysis catheters just before the administration of the final dose. Further dialysate samples of approximately 120  $\mu$ L each will be collected at 0 (just before administration of tedizolid dose), 1, 2, 3, 4, 5, 6, 7, 8, 9, 10, 11, 12, 16, 20, and 24 hours. After all sampling is complete, recovery of the antibiotic through the dialysis filter will be assessed by the retrodialysis technique over a 1-hour interval. All dialysate samples will be collected in 200  $\mu$ L microvials (CMA Microdialysis AB, Solna, Sweden), which will be additionally stored within amber-colored polypropylene tubes at -80 °C to protect against light and evaporation until concentration determination.

	
2.5.5.7 Protein Binding Analysis and Determination
 
Protein binding studies will be conducted using Centrifree® Ultrafiltration devices (Millipore Corporation, Billerica, MA).. An additional blood sample of 20 mL will be collected at the estimated peak concentration (3 hours after the dose was administered) into two 10-mL BD Vacutainer® tubes containing sodium heparin (green top). Samples will be immediately centrifuged to collect the separated plasma. Approximately 0.9 mL of plasma will be transferred into six separate ultrafiltration devices, three devices per filter type, and centrifuged for 45 minutes at 25 °C at 2,000 × g to generate an ultrafiltrate volume of approximately 250 µL. In addition, an aliquot of plasma will be retained for total drug concentration determinations and will be kept frozen at -80°C.
 
In addition, non-specific binding to the ultrafiltration membrane will be determined at a single tedizolid concentration similar to the peak observed in patients. For these studies, an aqueous standard of tedizolid will be prepared in accordance to manufacturer's recommendation and ultrafiltration will be performed as outlined above for both ultrafiltration devices..
 
Individual protein binding percentages will be applied to each participant's data at each time point to determine free plasma concentrations. The percentage of protein binding will be calculated using the following formula: % Protein Binding = 100 – (Concentrationultrafiltrate / Concentrationplasma × 100).
 
2.5.5.8 Study Exit Evaluation
 
After completion of all sampling and removal of microdialysis catheters, an end of study exit evaluation will occur. This will include a full physical examination, including vital signs. Blood and urine will be collected to repeat all labs tested in 2.5.5.1, except for the pregnancy test and drugs of abuse screening. All abnormal determinations will be followed until resolution unless follow-up is determined to be unnecessary by the study physician. For the control group, participants will be discharged from the study after a 4 hour monitoring period from removal of microdialysis catheters.
 
2.5.5.9 Determination of Tedizolid Concentrations
 
Tedizolid concentrations in plasma, dialysate fluid, and aqueous standards will be assessed using validated high performance liquid chromatography (HPLC) assays at the Center for Anti-Infective Research and Development of Hartford Hospital.

2.6 Study Duration	
IRB Submissions and Approval 2 months
 
Enrollment and Sampling of 10 Patients 6-12 months
 
Enrollment and Sampling of 6 Healthy Volunteers 4 months
 
Tedizolid HPLC 1 month
 
Pharmacokinetic Analysis 1 month
 
Final Report 2 months

2.7 Statistical Analysis and Sample Size Justification	
2.7.1 Data Validation and Analysis
 
The Principal Investigator will be responsible for the review, validation, and analysis of these data as collected and recorded by the study staff.
 
2.7.2 Primary Endpoint:
 
The primary endpoints of the study are to assess the penetration of tedizolid into infected skin tissue and compare it to the penetration into healthy skin tissue, as well as to assess the pharmacokinetics of tedizolid in plasma of both study populations.

	
2.7.2.1 Primary Endpoint Definition:
 
Percentage of tissue penetration of tedizolid will be defined based on the AUC in plasma and tissue and will be calculated as: <math>AUC_{\text{tissue}} / \text{free}AUC_{\text{plasma}} \times 100</math>. Plasma pharmacokinetic parameters that will be estimated including: <math>AUC_{0-24 \text{ (plasma)}}</math>, elimination rate constant (<math>K_e</math>), half-life (<math>t_{1/2}</math>), total plasma clearance (<math>CL_T</math>), and Volume of distribution (<math>V_d</math>).
 
2.7.3 Statistical Analysis
 
Non-compartmental pharmacokinetic analyses for tedizolid will be conducted using Phoenix (version 6.3, Pharsight Corporation, Mountain View, CA). Pharmacokinetic parameters for plasma will be determined using each individual's plasma concentration-time profile. The maximum concentration (<math>C_{\text{max}}</math>) for each participant will be estimated by visual inspection of the concentration-time profiles. The log-linear trapezoidal method will be used to determine <math>AUC_{0-24 \text{ (plasma)}}</math> for each participant. The elimination rate constant (<math>K_e</math>) will be estimated by the slope of the terminal portion of the concentration-time profile; half-life (<math>t_{1/2}</math>) will be calculated by <math>0.693/K_e</math>. Total plasma clearance (<math>CL_T</math>) will be calculated by Dose/<math>AUC_{0-24 \text{ (plasma)}}</math>. Volume of distribution (<math>V_d</math>) will be calculated by <math>CL_T/K_e</math>.
 
All microdialysis concentrations will be corrected for recovery before pharmacokinetic analysis as follows: <math>\text{Concentration}_{\text{tissue}} = 100 \times (\text{Concentration}_{\text{sample}} / \% \text{ in vivo recovery})</math>. The <math>AUC_{0-24 \text{ (tissue)}}</math> will be assessed by the log-linear trapezoidal rule. Percentage of penetration into tissue will be calculated as follows: <math>AUC_{\text{tissue}} / \text{free}AUC_{\text{plasma}} \times 100</math>.
 
A Student's t-test will be used to compare the penetration ratio and pharmacokinetics of tedizolid between study and control groups.
 
2.7.4 Sample Size Determination
 
Ten patients with diabetic foot infection (Study Group) and six healthy volunteers (Control Group) are to be enrolled in the study.
 
This is primarily a descriptive, controlled study to observe the exposure and penetration ratio of tedizolid into the interstitial fluid of infected tissue of diabetic patients and compare it to that of healthy volunteers. In similar study designs, 10 study patients were sufficient to describe the central tendency of these penetration estimates and some confidence of dispersion. Given reduced variability in healthy participants, 6 volunteers will be utilized.

2.8 Specific Drug Supply Requirements	
Tedizolid phosphate 200 mg tablets will be provided by Merck, Inc. as an open label supply.

2.9 Adverse Experience Reporting	
Participants will be monitored for any sign or symptom of adverse events throughout the course of the study. Unanticipated, life-threatening or fatal adverse events will be reported to the IRB, the manufacturer, and the Food and Drug Administration according to federal guidelines. All adverse events requiring medical attention will be treated by the study physician and will be recorded by the investigator.
 
2.9.1 Definitions
 
For the purpose of this study, an adverse event will be defined as any pathologic or unintended change in the structure (signs), function (symptoms), or chemistry (laboratory values) of the body associated with the use of the study drug, whether or

	
not considered drug related, and will be categorized as one of the following:
 
 
• MILD – present, but easily tolerated
 
• MODERATE – discomfort that interferes with usual activities
 
• SEVERE – incapacitating, inability to work or do usual activities
 
 
A serious adverse event will be defined as any of the above which results in death or is immediately life-threatening, requires in-participant hospitalization, or is an important medical event that may jeopardize the participant or require medical intervention to prevent one of the previously mentioned outcomes.
 
2.9.2 Relationship to Study Medication
 
Relationship of the adverse event to the study medication (i.e., causality) will be evaluated according to the investigator's opinion, as one of the following:
 
 
• Concurrent condition – unrelated to study drug
 
• REMOTE adverse drug event – little or no temporal relationship to study drug
 
• POSSIBLE adverse drug event – temporal relationship to study drug
 
• PROBABLE adverse drug event – commonly associated with study drug
 
• DEFINITE adverse drug event – reappeared on re-challenge of study drug
 
 
2.9.3 Expectedness of Adverse Event
 
As AEs are expected with the study medication, patients will be closely monitored throughout the study for any AE occurrence and will be managed accordingly by the study physician. All AEs will be recorded by the investigator as described in Section 2.9.4 below.
 
2.9.4 Recording and Reporting an Adverse Event
 
All adverse events requiring medical attention will be recorded by the investigator as such: categorization by severity (mild, moderate, or severe), established time frame (start and stop time), complete description of event, all interventions (medical and pharmacological), and causality.
 
2.9.5 Recording and Reporting a Serious Adverse Event (SAE)
 
All SAEs will be reported to the Institutional Review Board, sponsor, and the Food and Drug Administration according to Federal guidelines. A serious adverse event will be defined as any adverse event that results in death, is immediately life-threatening, requires or prolongs hospitalization, or is an important medical event that may jeopardize the participant or may require medical intervention to prevent one of the previously mentioned outcomes.

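### Does naming one ultrafiltration device but describing two filter types in section 2.5.5.7 leave the penetration endpoint undefined?

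*Combined protocol and SAP*

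**What the plan says.** Section 2.5.5.7 (Protein Binding Analysis and Determination) opens with a single product: "Protein binding studies will be conducted using Centrifree® Ultrafiltration devices". For this work, "An additional blood sample of 20 mL will be collected at the estimated peak concentration", taken as 3 hours after the dose. About 0.9 mL of plasma is then "transferred into six separate ultrafiltration devices, three devices per filter type", each spun to give roughly 250 µL of ultrafiltrate. An aliquot of plasma is kept for the total concentration.

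The section adds that "non-specific binding to the ultrafiltration membrane will be determined at a single tedizolid concentration similar to the peak observed in patients", using an aqueous standard, and that "ultrafiltration will be performed as outlined above for both ultrafiltration devices".

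Percentage binding is 100 minus the ultrafiltrate concentration as a percentage of the plasma concentration. Each participant's own percentage is applied "at each time point to determine free plasma concentrations". Sections 2.7.2.1 and 2.7.3 define penetration as tissue AUC over free plasma AUC, times 100. Section 2.7.3 compares the groups (10 patients, 6 volunteers) by Student's t-test.

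**The concern.** Two phrases imply two filter types and only one is named. If both types are run on every sample, each participant has two sets of ultrafiltrate values, while the formula has room for one. Neither 2.5.5.7 nor 2.7.3 says which set counts or how replicates combine. One percentage scales the whole plasma profile, so a difference between filters would not average out over time points. It would pass straight into the denominator of the primary endpoint, and the choice could in principle be made after the AUCs are known.

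A second gap sits beside the first. Non-specific binding to the membrane is measured, but the text gives it no use: no acceptance limit and no correction term. If membrane loss from plasma were material, the free fraction would be too low and penetration too high.

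**Working it through.** **1. Count and volume.** Filter types implied: 6 devices / 3 per type = 2. Types named: 1. The 0.9 mL must be per device, total 6 x 0.9 = 5.4 mL. Split six ways it would be 0.15 mL each, less than the 0.25 mL of ultrafiltrate expected. The six-device layout is therefore workable, and the conflict is only over the number of types.

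**2. If one filter is used.** Six is the printed device count, so there are six Centrifree results per participant and one retained plasma aliquot. Binding = 100 - 100 x `C_uf` / `C_plasma` is linear in `C_uf`. With a common `C_plasma`, averaging the six concentrations first or averaging six percentages gives the same answer. What remains wrong is a few leftover words.

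**3. If two filters are used.** Write penetration as 100 x `AUC_tissue` / (`fu` x `AUC_plasma`), with `fu` = (100 - B)/100 and B the percentage bound. If one filter reads B and the other reads d points lower, the two penetration values differ by the factor (100 - B + d)/(100 - B). The documents give neither B nor d, so both are assumed:

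| B (assumed) | d = 1 point | d = 2 points |
|---|---|---|
| 70% | 31/30 = 1.03 | 32/30 = 1.07 |
| 80% | 21/20 = 1.05 | 22/20 = 1.10 |
| 90% | 11/10 = 1.10 | 12/10 = 1.20 |

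For scale, the standard error of a mean of 10 patients is 20/√10 = 6.3% to 40/√10 = 12.6% of the mean, at an assumed CV of 20% to 40%. Five of the six factors are 1.10 or less.

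**4. Where the effect goes.** If the filters differ by a constant ratio, every participant's penetration is multiplied by the same number c. The difference in means becomes c times as large and so does the pooled standard deviation, so t and p do not change. The ratio of group means is also unchanged. Only the absolute percentage moves.

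A fixed gap in points does not cancel exactly if the groups differ in binding. At an assumed 80% in one group and 70% in the other, a 1-point gap shifts the ratio of means by 1.050/1.033 = 1.016, and a 2-point gap by 1.100/1.067 = 1.03. At 90% against 80% the shifts are 1.100/1.050 = 1.05 and 1.200/1.100 = 1.09.

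In 2.7 the prefix for free drug appears only in the penetration ratio. If plasma AUC, clearance, half-life and volume are computed from total concentrations, as that wording suggests, none of this touches them.

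**5. Non-specific binding.** If a fraction b of free drug is lost to the membrane, penetration is overstated by 1/(1 - b): 1/0.98 = 1.02 at an assumed 2%, 1/0.95 = 1.05 at 5%. A common b cancels in the t-test exactly as in step 4. Section 2.7.3 writes out the recovery correction for dialysate, so where the plan intends a correction it prints one. It prints none here, and the literal formula is complete without it.

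**The case for a change.** The strongest case for a change is that no reading leaves 2.5.5.7 correct as printed, and that the study is mainly descriptive, so the absolute penetration percentage is itself a headline result. A factor of 1.10 to 1.20 would matter to a reader of that figure. It would also be systematic, so comparing it with a standard error does not excuse it. A few sentences would close the gap, and an unstated choice of filter can be made with results in hand.

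The wording conflict stands in full: no other section resolves it and there is no redaction at that point. The larger factors, however, need high binding and a 2-point gap together, and nothing in the documents suggests that the filters disagree at all. Choosing the filter after seeing results would mean departing from the one device the section names. Nothing suggests that the groups would be handled differently, since the section describes one procedure for all participants. On non-specific binding, an aqueous standard may not reflect loss from plasma, so making it a mandatory correction would not clearly improve the estimate.

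**Conclusion.** No change to the plan follows. With one filter, this is a clerical slip in two phrases, and the six replicates give one defined percentage. With two, it is an unstated laboratory convention that would sensibly be filled by the named device's replicate mean, used identically in both groups. The possible effect on absolute penetration is a factor of 1.03 to 1.20, resting wholly on assumed binding of 70% to 90% and an assumed gap of 1 or 2 points. The between-group test is unaffected by a common proportional difference. It would be disturbed only if the filter or the loss differed between participants or groups, or, modestly, by a fixed point gap combined with unequal binding. The non-specific binding run is best read as a suitability check, and the binding formula is complete without it. Writing the choice down would be tidy, but the plan's calculation is not shown to be wrong.

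### The free fraction is measured at 25 °C but paired with a tissue AUC measured in vivo, so any temperature effect on protein binding would pass undetected into each group's absolute penetration percentage

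*Combined protocol and SAP*

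**What the plan says.** **Denominator.** Section 2.5.5.7 takes an extra plasma sample 3 hours after the dose, loads it into six ultrafiltration devices (three for each of two filter types), and has them "centrifuged for 45 minutes at 25 °C at 2,000 × g to generate an ultrafiltrate volume of approximately 250 µL". Percent binding is 100 minus the ultrafiltrate-to-plasma concentration ratio times 100. It is then used as follows: "Individual protein binding percentages will be applied to each participant's data at each time point to determine free plasma concentrations".

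**Numerator.** Section 2.5.5.6: "Interstitial fluid concentrations of the soft tissue in the lower extremity will be assessed by" in vivo microdialysis. Under the Microdialysis Procedure heading (the second section numbered 2.5.5.2), recovery is calibrated by retrodialysis through the implanted probe. Section 2.7.3 corrects every dialysate concentration for that recovery.

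**Endpoint.** Section 2.7.2.1: "Percentage of tissue penetration of tedizolid will be defined based on the AUC in plasma and tissue and will be calculated as" AUC_tissue / freeAUC_plasma × 100. Section 2.7.3 uses a Student's t-test to "compare the penetration ratio and pharmacokinetics of tedizolid between study and control groups".

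**Control on the ultrafiltration.** Section 2.5.5.7: "non-specific binding to the ultrafiltration membrane will be determined at a single tedizolid concentration similar to the peak observed in patients". This uses an aqueous standard put through the same procedure. The plan contains no 37 °C measurement, temperature correction, sensitivity analysis or reason for choosing 25 °C.

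**The concern.** The two halves of the ratio are measured under different conditions. Tissue concentrations and their recovery correction come from the living participant. The free fraction comes from a spin at 25 °C, which is 37 − 25 = 12 °C below body temperature. If tedizolid's protein binding changes over that interval, the free fraction used is not the one that applied in the circulation.

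Each participant has one free fraction, and it multiplies all of that participant's plasma concentrations. An error in it therefore rescales the whole denominator and does not average out over the sampling times. If the factor is shared, it does not average out over participants either.

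What is at stake is the absolute penetration percentage in each group. Section 2.7.4 describes the study as mainly descriptive, so these percentages are main results in their own right. Section 2.2 shows how such figures get used: it takes ratios of 1.1 and 1.2 from the earlier healthy-volunteer study as evidence of very good penetration.

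**Working it through.** The plan states no figure on this point to reproduce. The check is algebra, with assumed values where the documents are silent.

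**Inputs from the documents**
- Ultrafiltration temperature 25 °C; one binding value per participant, applied at all times (2.5.5.7).
- Penetration = 100 × AUC_tissue / freeAUC_plasma (2.7.2.1); AUC by the log-linear trapezoidal method (2.7.3).
- Group sizes 10 and 6 (2.7.4).

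**Not in the documents, so assumed:** tedizolid's bound fraction and how it changes with temperature.

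**Step 1: how the free fraction enters.** Let fu = C_ultrafiltrate / C_plasma. Multiplying every concentration by a constant fu multiplies a linear trapezoid, Δt(c₁ + c₂)/2, by fu. It does the same to a logarithmic one, Δt(c₁ − c₂)/ln(c₁/c₂), because the ratio inside the logarithm is unchanged. So freeAUC_plasma = fu × AUC_plasma exactly. A numerical check on an invented profile at the protocol's blood sampling times, with fu = 0.20, gave freeAUC/AUC = 0.20.

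**Step 2: effect on the endpoint.** Call the value obtained with fu at 37 °C the true penetration, and let k = fu(25 °C)/fu(37 °C). Then

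reported = 100 × AUC_tissue / (k × fu(37 °C) × AUC_plasma) = true / k.

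| Assumed k | True 100% reported as | True 110% reported as |
|---|---|---|
| 0.8 | 125.0% | 137.5% |
| 0.9 | 111.1% | 122.2% |
| 1.0 | 100.0% | 110.0% |
| 1.1 | 90.9% | 100.0% |
| 1.2 | 83.3% | 91.7% |

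The 110% column only borrows the scale of the adipose ratio of 1.1 in 2.2.

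**Step 3: dependence on the degree of binding (all values assumed).** Suppose measured binding is off by 2 percentage points.
- 2 points too high: 0.50/0.48 = 1.042 at 50% true binding, 0.20/0.18 = 1.111 at 80%, 0.10/0.08 = 1.250 at 90%. Penetration is inflated by 4.2%, 11.1% and 25.0%.
- 2 points too low: 0.50/0.52 = 0.962, 0.20/0.22 = 0.909, 0.10/0.12 = 0.833. Penetration is lowered by 3.8%, 9.1% and 16.7%.

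The same shift in percent bound matters more the more highly bound the drug is.

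**Step 4: the group comparison.** If k is the same for everyone, both means, their difference and the pooled SD are all divided by k, so t is unchanged. In one simulated data set of 10 versus 6, k = 0.8, 1.0 and 1.2 all gave a ratio of means of 0.9766, t = −0.2882 and p = 0.7774. Only the difference in points was rescaled (−3.20, −2.56, −2.13).

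If k differs by group, the study/control ratio is multiplied by k_control/k_study. For example, k = 0.8 in patients and 0.9 in volunteers gives 0.9/0.8 = 1.125. A milder assumed case uses a single-site model, fu = 1/(1 + b), with b proportional to binding-protein concentration. In volunteers, 80% bound at 25 °C and 75% at 37 °C means b = 4 and 3, so k = 0.20/0.25 = 0.80. With 30% less binding protein in patients, b = 2.8 and 2.1, so k = (1/3.8)/(1/3.1) = 0.816. The ratio is then multiplied by 0.80/0.816 = 0.98, a shift of about 2%.

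**Step 5: would the plan detect it?** The aqueous standard contains no plasma protein, so it cannot show a temperature effect on protein binding. The replicate devices and the two filter types are all spun at the same temperature, so they cannot show one either.

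**The case against.** The strongest reply is that no effect has been shown. The documents contain no bound fraction for tedizolid and no temperature data, and showing that an error would propagate if it existed can be done for any input to a ratio. The choice of 25 °C is explicit and contradicts nothing else in the plan. This stands: existence, direction and size are all unproven.

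Three stronger readings are tempting, and the documents support none of them.

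- **That penetration will be overstated.** This needs binding to be tighter at the lower temperature. Nothing in the documents says so for this drug, so the range has to run both ways and include zero effect.
- **That the result is judged against 100%.** The plan sets no benchmark, target or cut-off. Section 2.2 praises earlier ratios slightly above 1 but names no threshold.
- **That the patient-versus-volunteer comparison is compromised.** Both groups go through the same laboratory procedure, and a common k cancels from the ratio and from the t-test. Bias there requires k to differ between groups, which the documents do not indicate.

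In addition, total-plasma AUC, Ke, half-life, clearance and volume of distribution are calculated in 2.7.3 without the free fraction and are untouched.

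What survives is narrower. The absolute percentages carry an unchecked factor 1/k, the plan's control cannot detect it, and removing it takes little effort.

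**Conclusion.** The point holds as a conditional one. The free fraction is measured at 25 °C, the tissue AUC is measured in vivo, and any temperature effect on binding enters each participant's penetration percentage as 1/k with nothing in the plan to dampen or reveal it. For assumed k between 0.8 and 1.2, a true 100% would be reported anywhere from 125% down to 83%; with k = 1 there is no bias.

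The conclusion rests on two things from the documents (one constant free fraction per participant, and the ratio definition of the endpoint) and one assumption (the range of k). It concerns the absolute percentages in each group. It does not show that the planned percentages are biased, and it does not undermine the between-group test under a common k. It is a cheap improvement to the method.

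**What to change.** In 2.5.5.7, pre-warm the plasma and run the ultrafiltration at 37 °C. Run the aqueous non-specific-binding standard at the same temperature. Adjust the spin time so that the ultrafiltrate stays near 250 µL. This removes the mismatch whichever way an effect would go.

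If 25 °C is kept, run paired 25 °C and 37 °C ultrafiltration on a subset of the plasma already being collected, and report penetration under both free fractions. That measures k directly. Plasma volume needs a check: the planned set uses 6 × 0.9 = 5.4 mL, so a full second set would bring the need to 10.8 mL from a 20 mL blood draw, besides the aliquot kept for total drug. Dividing the devices between the two temperatures avoids this.

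The cost is a centrifuge setting, a pre-warming step, some method checking at the new temperature and possibly a change to the 45-minute spin. The main option uses the same blood samples, devices and assay, and nothing changes for participants.
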